8.3.1 Assessments for safety and effectiveness

DUSs are specifically designed to collect information about drug utilisation only. Any relationship between the drug and any adverse events are not within the scientific scope of these studies and therefore will not be collected.

8.3.2 Other assessments

Not Applicable

8.4 Data sources

Retrospective abstraction of data from patient medical records will be performed by trained healthcare professionals or external medical record abstractors. Data for each patient will be recorded in accordance with normal clinical practice and no additional assessments or tests considered as interventional will be required. Data obtained from the pilot study on physician (type of specialty), site (geographic location, practice type, size and patient volume) and patient (using retrospective abstraction of data from patient medical records) representativeness will be the basis for the feasibility assessment of the full DUS.

Concomitant medication with GLP-1 receptor agonists entered into the CRF will be coded using the WHO Drug Reference List.

Protocol		Date:	23 November 2015	Novo Nordisk
Study ID: NN8022-4241		Version:	5.0	
UTN: U1111-1185-3661		Status:	Final	
EU PAS No.:	CONFIDENTIAL	Page:	27 of 53	

All data will be entered pseudonymised into the CRF. See section 8.3 for the list of data to be collected; these data will be collected 6 months and 24 months after the launch of Saxenda[®], for the pilot and full study, respectively (see Figure 1).

The physician must keep a patient enrolment log and a log of patients evaluated for but not included in the study throughout the enrolment period. The log will include information on the number of patients approached to participate the study, the number of patients who accepted, the number of patients confirmed eligible, the number and reason patients were ineligible, and the number of patients who refused. These data will allow calculation of the participation rate. Each patient signing an informed consent form will be uniquely identified in the study by a patient identification number.

8.5 Study size

This is a descriptive study designed to examine in-market utilisation of Saxenda[®]/Victoza[®] and thus no hypothesis testing is planned and power calculations are not applicable. 100 patients will be enrolled for the pilot study, and an additional 300 patients will be enrolled for the full study.

8.6 Data management

A data management plan (DMP) will be created and will describe all functions, processes, and specifications for data collection, cleaning and validation for the DUS. High data quality standards will be maintained and processes and procedures utilized to repeatedly ensure that the data are as clean and accurate as possible when presented for analysis. Data quality will be enhanced through a series of programmed data quality checks that automatically detect out-of-range or anomalous data at the time of data entry.

Data management is the responsibility of ______. Appropriate measures such as encryption or deletion must be enforced to protect the identity of patients in all presentations and publications as required by local/regional/national requirements.

All data captured at sites will be collected and entered directly by a healthcare professional at the site or an external medical record abstractor into the CRFs. Each site will only have access to the patient data entered by the individual site. Appropriate measures such as encryption of data files must be used to assure confidentiality of patient data when it is transmitted over open networks.

8.6.1 Case report forms (CRFs) and rules for completing

All participating sites will have access to the data entered for subjects enrolled at their site. All site staff will be fully trained in CRF completion. Healthcare professionals and/or medical record abstractors will be responsible for entering extracted subject data into a secure web-based EDC database via CRFs. All CRFs should be completed by designated, trained personnel or the study

Protocol		Date:	23 November 2015	Novo Nordisk
Study ID: NN8022-4241		Version:	5.0	
UTN: U1111-1185-3661		Status:	Final	
ELI PAS No ·	CONFIDENTIAL	Page:	28 of 53	

coordinator or external data abstractor, as appropriate. The CRFs should be reviewed, signed, and dated by the investigator (or designee).

In most cases, the source documents are contained in the subject's medical record and data collected in the CRFs must match the data in the medical records. All original source documentation is expected to be stored at the site for the longest possible time required by local applicable regulations. The site will be instructed to notify the Sponsor before any destruction of medical records of study participants.

By signing the affirmation statement electronically, the physician confirms that the information is complete and correct.

8.6.2 Corrections to CRFs

CRF data can be corrected only by the physician, the physician's authorised staff or an external medical record abstractor. An audit trail will be maintained. If corrections are made by the physician's authorised staff after the date of the physician's signature on the affirmation statement, the statement must be signed again by the physician.

8.6.3 CRF flow

When data is entered, it will be available to Novo Nordisk and/or CRO for data verification activities.

When the final non-interventional study report is available, the data will be archived by Novo Nordisk.

8.7 Data analysis

All data analysis will be performed by

As this is a descriptive study that will investigate in-market utilisation of liraglutide, no formal statistical testing will be conducted.

Characteristics of study participants will be reported as mean, standard deviation, median, first and third quartiles and range for continuous variables and as number and proportion of patients with observed (non-missing) data for categorical variables. Study participation will be presented, including number of sites approached for the study and response rate, by specialty, and number of patients approached, response rates, and reasons for refusal. Characteristics of the participating sites and patients will be presented, stratified by country. The data may also be evaluated and presented for other meaningful subgroups of patients (e.g., by sex or age). Comparison between participants and non-participants will be made for sites and patients. Participating and non-participating sites will be compared on geographic location, area of primary practice, practice type, practice size and

Protocol		Date:	23 November 2015	Novo Nordisk
Study ID: NN8022-4241		Version:	5.0	
UTN: U1111-1185-3661		Status:	Final	
FILPAS No.	CONFIDENTIAL	Page.	29 of 53	

patient volume. Comparison of participating patients and the total population of patients treated with Saxenda[®] or Victoza[®] will be made, subject to data availability.

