8.1 Study design

8.1.1 Type of study

This DUS is a non-interventional, multi-centre Post Authorisation Safety Study (PASS) to investigate the use of Saxenda[®] and Victoza[®] in clinical practice in patients who have initiated treatment in the Saxenda[®] postmarketing period. The DUS involves retrospective review of patients' medical records in two selected European Union (EU) countries 24 months after launch of Saxenda[®] in each of the countries. Physician sampling will be built using several tools, including intelligence databases, e.g., IMS LifeLinkTM, in order to obtain a representative sample of Saxenda[®]/Victoza[®] prescriptions according to physician specialty and geography. This data source will be complementary to the full study and will be obtained on a quarterly basis, during the study period. It will provide, on a national level for the two targeted countries, the distribution of sites and prescribers' specialty. It will not identify individual prescribers, but rather guide the site selection for the study performed by Therefore, IMS LifeLinkTM will be used a priori to refine the sampling strategy (using regional and specialty distribution of prescribers), and a posteriori to assess the representativeness of prescribers and patients, for both the pilot and full study.

A case report form (CRF), including all the desired data elements, will be available to the selected sites; one CRF is to be completed per patient prescribed Saxenda® or Victoza®. The CRF may be completed by a trained healthcare professional at the site, or by a trained external medical record abstractor. The data will be entered pseudonymised into the CRFs.

A pilot study, to be embedded in the full study, will be conducted 6 months after launch of Saxenda[®] in each of the two countries, i.e., prior to the full DUS. The objective of the pilot study is to evaluate the feasibility of the full DUS. The feasibility will be evaluated on three main parameters:

- 1. Possibility of identifying physicians prescribing Saxenda®/Victoza® and participating sites
- 2. Possibility of identifying patients treated with Saxenda® or Victoza®

Protocol		Date:	23 November 2015	Novo Nordisk
Study ID: NN8022-4241		Version:	5.0	
UTN: U1111-1185-3661		Status:	Final	
EU PAS No.:	CONFIDENTIAL	Page:	19 of 53	

3. Availability and quality of the variables used to determine the specified endpoints (see section 7.3)

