8.2 Setting

Since the purpose of this study is to investigate real-world, in-market utilisation of liraglutide, patients will be identified based on the prescription rather than on a specific diagnosis. The study will target first-time patients of Saxenda® or Victoza® by identifying a representative sample of physicians who treat diabetic or obese patients for whom Saxenda® or Victoza® can be prescribed. These include general practitioners (GPs), endocrinologists and cardiologists (or other diabetes and obesity specialists) from a variety of settings (e.g., office-based vs. hospital-based, urban vs. rural). Once prescribers of Saxenda® or Victoza® are identified, these will be oversampled to ensure adequate numbers of prescribers (and therefore patients).

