8.2.2 Inclusion criteria

To be eligible for the study, patients will be required to meet both of the following inclusion criteria:

1. Initiation of Saxenda® or Victoza® (initiation is defined as no prescription of the same brand within the previous 12 months).

Protocol		Date:	23 November 2015	Novo Nordisk
Study ID: NN8022-4241		Version:	5.0	
UTN: U1111-1185-3661		Status:	Final	
EU PAS No.:	CONFIDENTIAL	Page:	22 of 53	

2. Informed consent obtained before any study-related activities. Study-related activities (e.g. data collection) are any procedures that are carried out as part of the study, including activities to determine suitability of the study.

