8.9 Limitations of the research methods

As this is a non-interventional study, potential bias cannot be ruled out.

Data collection will reflect routine clinical practice rather than mandatory ass

Data collection will reflect routine clinical practice rather than mandatory assessments at prespecified time points, which may have an impact on the amount of data available and its interpretation.

Biases

Selection bias

 Protocol
 Date:
 23 November 2015
 Novo Nordisk

 Study ID: NN8022-4241
 Version:
 5.0

 UTN: U1111-1185-3661
 Status:
 Final

Page:

35 of 53

In order to minimize selection bias, the sampling strategy that was designed for the proposed study, will truly reflect real-life clinical practice since it will capture all possible treatment settings. In addition, selection bias due to sampling and participation will be addressed by comparing selected characteristics of the study patients and prescribers with those recorded in an external national database (IMSLifeLink).

Information bias

EU PAS No .:

At the prescriber (site) level, information bias is mitigated by the retrospective design. This study involves no intervention and treatment of patients considered eligible and their medical records at a site have been completed prior to the country-specific index date. Thus, the knowledge about this study (and its conduct) will not have had impact on the standard medical care and Saxenda® or Victoza® prescription practices at a site and will not have affected the treatment of patients. Data collected from medical records will therefore reflect real world medical practice.

At the patient level, misclassification of drug exposure has to be considered. Medical records provide detailed information on prescribed and/or dispensed medications but may not contain information on the intended duration of use (days of supply) and often do not contain information on the actual use of the medications by the patient. Thus, patients may be classified as exposed to a drug although they actually have not taken the drug. For this reason, great care will be taken to ensure the quality of the information that is abstracted, and prescribers' follow-up by clinical research associates (CRAs) will be enforced.

Missing Data

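### The Victoza patient comparison in section 8.7 sets initiators against all treated patients, so it cannot be read as evidence for or against selection bias

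*Protocol*

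**What the plan says.** **Who is studied.** Section 8.2 states: "The study will target first-time patients of Saxenda® or Victoza". Section 8.2.2 makes this operational: "initiation is defined as no prescription of the same brand within the previous 12 months". Section 8.2.6 sets the data collection period, for both brands, from Saxenda launch to the index date. Section 8.1.1 puts that date at 6 months after launch for the pilot and 24 months for the full study.

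**Who they are compared with.** Section 8.7 plans a "Comparison of participating patients and the total population of patients treated with" either brand, which "will be made, subject to data availability". Nothing in the protocol limits this reference group to initiators.

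**What the external comparison is for.** Section 8.1.1 uses a national prescription database "a posteriori to assess the representativeness of prescribers and patients", in the pilot and in the full study. Section 8.9 says that "selection bias due to sampling and participation will be addressed by comparing selected" characteristics of study patients and prescribers with those in an external national database.

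**Time on the market.** Section 6 dates the EU authorisation of Victoza to June 2009 and that of Saxenda to March 2015.

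**The concern.** A check for selection bias compares the sample with the population it was meant to be drawn from. Here the sample comes from initiators, while the reference named in section 8.7 is everyone treated.

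For Saxenda this hardly matters, since the window opens at launch and nearly every treated patient is an initiator. For Victoza the reference also includes patients already on treatment when the window opens. Most of them cannot enter the study; the exception is a patient who stops and restarts after a gap of more than 12 months.

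Continuing users may differ from initiators. One reason lies in the protocol itself: section 8.1.3 describes stepwise dose increases from a starting dose, so at any given moment the two groups can be at different doses. A sample that represents Victoza initiators perfectly could then look unrepresentative, and a skewed sample could look sound. What is at stake is the statement about representativeness for the first secondary objective, not the estimate itself. Section 8.4 also bases the feasibility assessment of the full study partly on patient representativeness in the pilot.

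**Working it through.** **1. The plan's own figure.** Sections 3.7 and 8.2.1: 2 × (25 + 25) = 100 for the pilot and 2 × (75 + 75) = 300 for the full study, 400 in all. This reproduces. The point does not depend on it, and section 8.5 gives no power calculation to check.

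**2. The identity.** For any compared characteristic, let p_I be its proportion among Victoza initiators, p_C its proportion among ineligible continuing users, c the share of such users in the treated population, and b the true selection bias of the sample relative to initiators.

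- Sample: p_I + b
- Reference in section 8.7: (1 − c)·p_I + c·p_C
- Observed gap: b + c·(p_I − p_C)

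If b = 0, the gap is c·(p_I − p_C), a false signal. If b = −c·(p_I − p_C), the gap is zero and the bias is hidden. With a reference limited to initiators, c = 0 and the gap equals b.

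**3. Size under assumed ranges.** The protocol gives neither c nor the difference d = |p_I − p_C|. Both are assumptions here. The artefact c × d, in percentage points:

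| c | d = 5 | d = 10 | d = 20 |
|---|---|---|---|
| 30% | 1.5 | 3 | 6 |
| 50% | 2.5 | 5 | 10 |
| 70% | 3.5 | 7 | 14 |
| 90% | 4.5 | 9 | 18 |

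**4. Where c might lie.** The section 5 milestones and the index dates imply a Saxenda launch in about April to May 2016 (April 2018 less 24 months; November 2016 less 6 months). June 2009 to April 2016 is 82 months, or 6.83 years. Assume constant Victoza initiation at rate r, exponential discontinuation at rate L per year, no restarts, and national marketing from the EU authorisation date.

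- On treatment at launch: r(1 − exp(−6.83L))/L
- Initiating in the 24-month window: 2r
- L = 0.2: 3.73/(3.73 + 2) = 65%
- L = 0.5: 1.93/(1.93 + 2) = 49%
- L = 1.0: 1.00/(1.00 + 2) = 33%

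At d = 10 points the artefact is 3.3 to 6.5 points; at d = 15 it is 5.0 to 9.8. Over the pilot's 6-month window (0.5r new patients) the same model gives c of about 67% to 88%.

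**5. Scale.** The 95% half-width, 1.96·√(p(1 − p)/n), for p from 10% to 50% is 4.8 to 8.0 points with 150 Victoza patients and 6.8 to 11.3 points with 75 per country. The artefact is below sampling error over much of the range and can match or exceed it at the upper end.

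**The case against.** **The link between sections is inferred.** Section 8.7 names neither the source nor the purpose of its comparison. Section 8.9 names both but does not say all treated patients. The total population may mean national as opposed to sampled, and section 8.7.2 leaves analysis details to a statistical analysis plan that is not at hand. This stands, and the point is conditional for that reason. Still, the only reference population for patients that the protocol names is the total treated one. The clause on data availability decides whether the comparison is made, not who is in it.

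**Other checks exist.** Section 8.7 also compares participants with non-participants. Section 8.4 requires logs of patients approached, accepting and refusing, and section 8.3 records invited sites and reasons for refusal. This stands in part: for patients, these checks address participation within a site, not which sites and prescribers were sampled.

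**The fix may not be feasible.** Section 8.1.1 describes the database as giving the distribution of sites and prescriber specialties. Nothing shows that it can look back 12 months for individual patients. The fix therefore needs a fallback.

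**Stronger readings that the protocol does not support.**

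- A reader might infer that no earlier Victoza user can enter. The 12-month rule admits those restarting after a longer gap.
- A reader might infer that the claim of generalisability collapses. Section 8.2.5 rests that claim on the sampling approach and the selection criteria, and aims it at all subjects prescribed either brand. For that wider target, a comparison with all treated patients has descriptive value.
- A reader might take the remark in section 8.9 about several treating specialists as evidence that continuing users differ. It concerns incomplete records.

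**Conclusion.** The mismatch holds for Victoza and is negligible for Saxenda. If the section 8.7 comparison is the one that sections 8.1.1 and 8.9 rely on, its Victoza result mixes selection bias with the difference between initiators and continuing users, and cannot be cited for or against bias from sampling and participation.

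The size is not known. The 1.5 to 18 points, and the narrower 3 to 10 points from the market model, rest wholly on assumed shares and differences and on a launch date inferred from the milestones. They show what could happen, not what will.

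The Victoza endpoint is a count among participants and is unaffected. Since the study is descriptive and partial safeguards exist within sites, the severity is minor.

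**What to change.** 1. In section 8.7, with matching wording in sections 8.1.1 and 8.9, define the reference for the selection-bias check as patients initiating the brand between Saxenda launch and the index date, under the same 12-month rule, by brand and country.
2. A comparison with all treated patients may stay, but only as a description of how initiators differ from the wider population named in section 8.2.5.
3. If the database cannot isolate Victoza initiators, state that the Victoza comparison cannot separate selection bias from the initiator/continuing-user difference, and do not cite it either way.

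The cost is one sentence in section 8.7, conforming wording in the two other sections, and a new-user filter on the external extract. The downside is a smaller Victoza benchmark, or none where a 12-month look-back is impossible. The sample size stays at 400.

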8.7.1 Evaluability of patients for analysis

The full analysis set (FAS), including all recruited patients, will be analysed in the study.

8.7.2 Statistical methods

Details of the data analyses, along with table, listing and figure (TLF) templates, will be fully described in a Statistical Analysis Plan (SAP).

In brief, the descriptive analyses will present Saxenda[®] and Victoza[®] utilisation by indication. Results will be evaluated by site characteristics, including country and geographic region within country, to ascertain any patterns of prescribing by specific indication. The main analysis will be to estimate the proportion of prescriptions outside label among Saxenda[®] or Victoza[®] patients during the entire study period in the countries of interest. The proportion of each of the forms of prescription outside label will be described (see section on prescription outside label). Characteristics of patients prescribed Saxenda[®] or Victoza[®] according to the respective approved SmPCs will also be evaluated.

Analyses on the following will be conducted:

Site characteristics

Descriptive statistics will be provided for the following variables:

- Geographic location of physician site (number and proportion)
- Specialty or area of primary practice (e.g. GPs, cardiologists, endocrinologists (or other diabetes and obesity specialists), etc.) (number and proportion)
- Practice type (e.g. community hospital, academic/medical centre, office based, etc.) (number and proportion)
- Number of physicians who practice at site (mean, standard deviation, median, first and third quartiles and range)
- Patient volume (i.e. number of patients and estimated number of patients using Victoza[®] or Saxenda[®]) (mean, standard deviation, median, first and third quartiles and range)

Patient demographics, medical history, and other characteristics:

Descriptive statistics will be provided for the following variables:

- Age (mean and standard deviation; number and proportion for age categories)
- Sex (number and proportion)

Protocol		Date:	23 November 2015	Novo Nordisk
Study ID: NN8022-4241		Version:	5.0	
UTN: U1111-1185-3661		Status:	Final	
EU PAS No.:	CONFIDENTIAL	Page:	30 of 53	

Drug utilisation:

Descriptive statistics will be provided for the following variables:

Saxenda® or Victoza® patients:

- Brand name (number and proportion)
- Indication prescribed at treatment initiation (number and proportion)
- Target dose prescribed at treatment initiation (number and proportion for target dose categories: 3.0 mg/day (for Saxenda® patients) and 1.2 mg/day, 1.8 mg/day or 3.0 mg/day (for Victoza® patients)

Saxenda® patients only:

- Comorbidities:
 - Dysglycaemia (T2DM or prediabetes), hypertension, dyslipidaemia, and/or obstructive sleep apnoea (number and proportion)
- Dose at 4-12 weeks and 16-24 weeks post initiation of treatment (mean, standard deviation)
- Duration of treatment (or ongoing treatment) (mean, standard deviation, median, first and third quartiles and range; number and proportion for treatment completion: completed treatment or ongoing treatment)

Victoza® patients only:

- Increase in Victoza® dose to 3.0 mg/day (number and proportion)
- Prescription of Victoza® for weight management (number and proportion)

Prescription outside label:

Descriptive statistics for the following:

Saxenda® patients:

- BMI<27 kg/m² (number and proportion)
- 27 kg/m²≤BMI<30 kg/m² and no relevant comorbidities registered (dysglycaemia (T2DM or prediabetes), hypertension, dyslipidaemia, and/or obstructive sleep apnoea) (number and proportion)
- BMI not measured within 6 months before date of first prescription (number and proportion)
- Non-adherence to dose escalation according to label (i.e., 3.0 mg not reached within 4-12 weeks after date of first prescription) (number and proportion)
- Non-adherence to stopping rule (i.e., less than 5% weight loss after 16-24 weeks on Saxenda® 3.0 mg and still on continued treatment) (number and proportion)

Protocol		Date:	23 November 2015	Novo Nordisk
Study ID: NN8022-4241		Version:	5.0	
UTN: U1111-1185-3661		Status:	Final	
EU PAS No.:	CONFIDENTIAL	Page:	31 of 53	

• Concomitant medication with other GLP-1 receptor agonists (brand name) (number and proportion)

Victoza® patients:

- Dose information of 3.0 mg per day (number and proportion)
- Prescribed indication of weight management (number and proportion)

All analyses will be performed using SAS 9.2 (or higher) statistical software (SAS Institute Inc., Cary, North Carolina, USA). Programs, logs, and output will be reviewed for accuracy according to relevant standard operating procedures.

